**Effect of Chronic Exenatide Therapy on Beta Cell Function and Insulin Sensitivity in T2DM**

## **Study A.**

**Subjects:** 80 T2DM subjects (age = 18-70 years; BMI = 21-45 kg/m^2; male or female) according to the ADA criteria will participate in the study. Subjects must be drug naïve and/or on a stable dose (more than 3 months) of metformin and/or sulfonylurea and have HbA1c >7.0% and <10.5%. Subjects taking drugs known to affect glucose metabolism (other than metformin and sulfonylurea) will be excluded. Other than diabetes, subjects must be in good general health as determined by physical exam, medical history, blood chemistries, CBC, TSH, EKG and urinalysis. Only subjects whose body weight has been stable ( $\pm$  3 lbs) over the preceding three months and who do not participate in an excessively heavy exercise program will be included. Individuals with evidence of proliferative diabetic retinopathy, plasma creatinine >1.4 females or >1.5 males will be excluded. Diabetic subjects will be recruited from the South Texas Veterans Health Care System and Texas Diabetes Institute (TDI) in San Antonio (Deputy Director = [name]). TDI is the largest institute in the United States that provides comprehensive care for ~ 10,000 unduplicated T2DM patients. Therefore, we do not anticipate any problem in recruiting the required number of patients for this study.

**Study design:** After screening, eligible subjects will receive a measurement of endogenous glucose production (EGP) with a prime-continuous infusion of 3-H-glucose. The EGP measurement will be performed in the morning after a 10-12 hour overnight fast and will last 8.5 hours (from 6 AM to 2:30 PM). After a 3.5-hour tracer equilibration period, subjects (20 per group) will receive one of the following medications: (i) placebo; (ii) exenatide 5 ug subcutaneously; (iii) dapagliflozin (10 mg); and (iv) dapagliflozin 10 mg plus exenatide 5 ug (see flow diagram on page 11). Following the test medication at 9:30 AM, blood samples will be drawn every 10-20 minutes for an additional 5 hours and plasma glucose, insulin, C-peptide, glucagon concentrations and glucose specific activity will be measured. One-two weeks after the EGP measurement, participants will come back for the Double Tracer Oral Glucose Tolerance Test (DT-OGTT).

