**Data Analysis and Statistical Methods:** The **primary end point** of the study is the change in EGP during **Study A**. The difference in the rate of EGP during the last hour of the study (i.e. from 240-300 minutes) between drug-treatment and placebo-treatment studies represents the effect of drug treatment on EGP. The difference in EGP will be compared among the 3 drug treatments (exenatide, dapagliflozin, and exenatide plus dapagliflozin) with ANOVA. Post hoc testing will be performed with a Bonferroni correction for multiple

comparisons. The following primary comparison will be performed: (i) the change in EGP above baseline following dapagliflozin alone versus dapagliflozin/exenatide. The following secondary comparisons will be made: (i) the change in EGP above baseline following exenatide alone versus dapagliflozin/exenatide and (ii) the change in EGP above baseline following dapagliflozin alone, exenatide alone, and dapagliflozin/exenatide versus the change in EGP following placebo. Between group comparisons will be made with repeated measures ANOVA with time and treatment group as factors.

**Other secondary end points** will be: (i) the decrement in the fasting plasma glucose conc at the end of the study compared to baseline, (ii) change in plasma glucagon conc at the end of the study compared to baseline; and (iii) change in plasma insulin conc at the end of the study compared to baseline. Secondary end points will be compared using the same statistical methods described for the primary end point.

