**Anticipated Results and Data Interpretation.** Consistent with our published data (10), we anticipate that EGP will decrease progressively following placebo administration while, after an initial decline, EGP will increase progressively following dapagliflozin. We anticipate that plasma glucagon conc will increase and plasma insulin concentration will decrease following dapagliflozin administration. We anticipate that a single administration of exenatide will cause an increase in plasma insulin conc and a decrease in plasma glucagon conc compared to placebo. The increase in plasma insulin and decrease in plasma glucagon conc following exenatide administration will result in a greater decline in both EGP and fasting plasma glucose conc compared to placebo. Most importantly, we anticipate that the increase in plasma glucagon conc, the decrease in plasma insulin conc, and rise in EGP following dapagliflozin administration will be prevented, at least in part, if not totally, when exenatide is co-administered with dapagliflozin. Therefore, we anticipate an additive, even synergistic, decrease in plasma glucose conc and EGP following co-administration of dapagliflozin plus exenatide compared to either drug alone.

**Sample Size Calculation:** In our published results (10), the difference in the rate of basal EGP during the last hour of EGP measurement in dapagliflozin-treated and placebo-treated individuals was  $0.70 \pm 0.34$  (mean  $\pm$  SD). To detect a 50% decrease in the difference at alpha = 0.005 ( $=0.5/10$ ) (split alpha for up to 10 multiple comparisons and a Bonferroni correction) in exenatide plus dapagliflozin versus dapagliflozin alone, we computed that 17 subjects in each group provided 90% power. To ensure 17 completers assuming 15% lost to follow-up, we have set the sample size at 20 ( $=17/0.85$ ) in each group.

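### Study A's insulin endpoint: fix the analysis scale in advance. A baseline-adjusted log-scale analysis is the better default if insulin responses scale with baseline, and loses power if they do not

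*Combined protocol and SAP*

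**What the plan says.** Under Study A, Data Analysis and Statistical Methods, the other secondary endpoints include the "change in plasma glucagon conc at the end of the study compared to baseline" and the "change in plasma insulin conc at the end of the study compared to baseline". The method is inherited: "Secondary end points will be compared using the same statistical methods described for the primary end point". For EGP that means ANOVA, Bonferroni-corrected post hoc tests, and this statement: "Between group comparisons will be made with repeated measures ANOVA with time and treatment group as factors". No log scale, ratio, percentage change, baseline covariate or check of distribution is mentioned. An absolute change in concentration is the natural reading, although the text does not call it absolute.

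The Subjects paragraph admits patients who are "drug naïve and/or on a stable dose (more than 3 months) of metformin and/or sulfonylurea and have HbA1c >7.0% and <10.5" per cent, with BMI 21-45 kg/m². No stratification is stated.

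Anticipated Results and Data Interpretation gives directions of effect only: "plasma glucagon conc will increase and plasma insulin concentration will decrease following dapagliflozin administration", and a single exenatide dose is expected to "cause an increase in plasma insulin conc and a decrease in plasma glucagon conc compared to placebo". There is no mean, SD, CV, effect size or power for either hormone.

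The sampling table for the glucose turnover study has repeated insulin samples before time zero, and late samples at 260, 280 and 300 minutes.

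**The concern.** The methods were written for EGP, the only outcome with a stated SD, and were carried over to hormones without comment. Fasting insulin in so mixed a group is likely to be widely spread and right-skewed. If a drug changes insulin by a given percentage, a subject with a high starting value contributes a large absolute change and a subject with a low one a small change. An ANOVA of absolute changes then gives most influence to a few high-insulin subjects, and a baseline covariate on the same scale does not cure this.

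The insulin result is part of the mechanism that the trial sets out to show: exenatide is expected to offset dapagliflozin's effects on insulin, glucagon and EGP. Lost precision there would leave an EGP result harder to explain. Leaving the scale open also allows it to be chosen after the results are known.

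**Working it through.** **Inputs from the documents.** 20 per group, 17 expected to complete, and alpha 0.005 ("To detect a 50% decrease in the difference at alpha = 0.005"; Study A, Sample Size Calculation). There is no insulin power figure to reproduce. The only Study A figure is 17 per group for EGP. With difference 0.35, SD 0.34, two-sided alpha 0.005 and 90% power, the two-sample formula gives 2(0.34/0.35)²(2.807 + 1.282)² = 31.6, so 32 per group. That mismatch is a separate matter and is not used here.

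**Assumptions (not in the documents).** Lognormal baseline with median 1 and CV 40-80%; end/baseline ratio 0.85 in one arm and 0.85 × 1.3 = 1.105 in the other; within-subject log-SD 0.25; two arms of 20; two-sided alpha 0.05.

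**Proportional response, log scale.** Difference ln 1.3 = 0.262. SE = 0.25√(2/20) = 0.0791. Power ≈ Φ(0.262/0.0791 − 1.96) = Φ(1.36) = 91%, whatever the baseline CV.

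**Proportional response, absolute change, CV 60%.** Write change = b(rε − 1).
- For baseline b, E(b) = √1.36 = 1.166 and E(b²) = 1.36² = 1.850. For noise ε, E(ε) = e^0.03125 = 1.032 and E(ε²) = e^0.125 = 1.133.
- With r = 0.85: mean change −0.143, variance 0.099.
- With r = 1.105: mean change 0.163, variance 0.165.
- Difference 0.307. SE = √((0.099 + 0.165)/20) = 0.115. Power ≈ Φ(2.67 − 1.96) = 76%.

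**Additive response, absolute change.** The shift is 1.105 − 0.85 = 0.255, with constant noise of 0.25 of the median baseline. Power ≈ Φ(0.255/0.0791 − 1.96) = Φ(1.26) = 90%, whatever the baseline CV.

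**Simulation.** This replaces the normal approximation with t tests and log-scale ANCOVA:

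| True response | Analysis | CV 40% | CV 60% | CV 80% |
|---|---|---|---|---|
| Proportional | Absolute change | 84-85% | 78-79% | 74-75% |
| Proportional | Log scale | 88-91% | 88-91% | 88-91% |
| Additive | Absolute change | 88-89% | 88-89% | 88-89% |
| Additive | Log scale | about 79% | 73-75% | about 68% |

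In the proportional case at CV 60%, adding baseline as a covariate on the concentration scale gives 77%, so the gain comes from the scale. With log-SD 0.35, absolute-change power over the three CVs is 55%, 52% and 46%, against 61-64% on the log scale.

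**Closer to the plan's design.** Four arms, 17 completers each, two-sided alpha 0.005, combination versus dapagliflozin, log-SD 0.25. Assumed end/baseline ratios for insulin are 0.90, 1.25, 0.80 and 1.00 (placebo, exenatide, dapagliflozin, combination). At CV 50%, moving from absolute change to log ratio takes power from 18% to 39% if the response is proportional, and from 29% to 22% if it is additive.

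**Glucagon, same design.** Assumed ratios are 0.95, 0.85, 1.15 and 0.95. With a proportional response, power goes from 29% to 26% at CV 20%, 27% to 26% at CV 30%, 22% to 26% at CV 50% and 13% to 26% at CV 90%. With an additive response at CV 50% it goes from 30% to 9%.

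**Validity.** With no treatment effect, the absolute-change test rejects between 4.2% and 4.9% of the time at nominal 5%.

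**The case against.** The strongest objection is that a model with proportional response and proportional noise builds in the advantage of the log scale. With an additive response and constant noise the sign reverses, by a margin at least as large. The documents cannot say which model is nearer the truth. This stands, and it is why the point is conditional.

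A reader might also infer three stronger things, none of which the documents support:
- **That the planned ANOVA is invalid because its equal-variance assumption fails.** Nothing in the documents shows the variances, and in simulation the type I error is held. The question is one of efficiency.
- **That glucagon should be handled the same way.** The argument from BMI and sulfonylurea use is about insulin. For glucagon the gain is small or absent below a CV of about 50%, even under a proportional response.
- **That the log scale should extend to C-peptide and the DT-OGTT measures.** No analysis supports this for C-peptide. The secretion indices under Visit 3 are ratios of increments, which can be zero or negative and then have no logarithm.

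Two limits of the check also stand. It models one end value, whereas the plan also names a repeated measures ANOVA over time. And where within-subject noise is larger (log-SD 0.35), the log scale still reaches only 61-64%, so it improves the insulin endpoint without making it well powered.

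**Conclusion.** The point holds for insulin, as a conditional and inexpensive improvement. The plan commits to a concentration change with no baseline covariate in a population where fasting insulin is likely to be widely spread, and gives no reason for that scale. Under a proportional response, log analysis gains about 10 percentage points at the central assumptions (79% to 88-89%). Under an additive response it loses about 13 to 15 (88% to 73-75%). The CVs, log-SDs, effect sizes and form of response are all assumptions. A proportional response is reasonable for fasting insulin here but unproven, so it would be wrong to conclude that a log analysis must raise power, or that the planned test is unsound.

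**What to change.** Before outcome data are examined by arm:
1. Check the scale in the sponsor's earlier dapagliflozin data, if insulin was measured there, or in this trial's baseline data with arm labels hidden. Baseline spread shows how much the choice matters. Whether within-subject variation rises with a subject's level, seen in the repeated pre-dose samples, helps show which way it goes.
2. Unless that check points to an additive response, define the insulin endpoint as log(end/baseline). Compare arms by ANCOVA with log baseline as covariate and report geometric mean ratios with 95% CI. Report the baseline-adjusted absolute change as a sensitivity analysis.
3. Define both time points. For the end, average the 260, 280 and 300 minute samples; the plan's 240-300 minute window is stated for EGP only, and no insulin sample is scheduled at 240. For baseline, average named pre-dose samples. The sampling table places dapagliflozin at −30 minutes, while the Study design paragraph places the test medication at 9:30 AM, after 3.5 hours of tracer. These must be reconciled before the samples from −20 to 0 can be called pre-dose.
4. For glucagon, keep the concentration scale and add baseline as a covariate, unless the same check shows a wide spread. Leave the DT-OGTT increment indices as they are.

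The cost is analysis-plan wording and a short data check, with no new samples. The insulin estimand becomes a ratio, read as a percentage difference, and power is lost if the response proves additive.

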**Sample Size Calculation:** In our published results (10), the difference in the rate of basal EGP during the last hour of EGP measurement in dapagliflozin-treated and placebo-treated individuals was  $0.70 \pm 0.34$  (mean  $\pm$ SD). To detect a 50% decrease in the difference at alpha = 0.167 ( $=0.5/3$ ) (split for 3 comparisons and a Bonferroni correction) in Byetta plus dapagliflozin versus dapagliflozin alone, we computed that 13 subjects in each group will provide 90% power.

**Data Analysis:** In **Study C**, we anticipate that dapagliflozin and Bydureon will produce similar reductions in HbA1c and that the combination of dapagliflozin plus Bydureon will produce an additive/near-additive reduction in A1c. We anticipate that both dapagliflozin and Bydureon monotherapy will produce significant weight loss and that the combination will produce an additive, even synergistic, effect on weight loss.

We anticipate that that the dapagliflozin-induced rise in EGP will persist after 4 months in T2DM patients receiving dapagliflozin monotherapy even though both beta cell function and peripheral insulin sensitivity improve. We expect that Bydureon-treated T2DM patients will experience a reduction in both fasting and postprandial plasma glucose levels during the OGTT, markedly enhanced beta cell function, improved peripheral tissue insulin sensitivity, and reduced fasting and postprandial plasma glucagon concentrations during the DT-OGTT. In T2DM patients receiving combined Bydureon-dapagliflozin therapy, we hypothesize that exenatide will block the dapagliflozin-induced rise in glucagon secretion and overcome the dapagliflozin-induced decrease insulin secretion, resulting in suppression of EGP. Because we anticipate that Bydureon will offset the negative effects of dapagliflozin on EGP and on insulin and glucagon secretion, we expect that the decline in fasting and postprandial glucose concentrations during the DT-OGTT will be enhanced in T2DM subjects receiving combination Bydureon/dapagliflozin therapy.

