**Sample Size Calculation:** In our published results (10), the difference in the rate of basal EGP during the last hour of EGP measurement in dapagliflozin-treated and placebo-treated individuals was  $0.70 \pm 0.34$  (mean  $\pm$ SD). To detect a 50% decrease in the difference at alpha = 0.167 ( $=0.5/3$ ) (split for 3 comparisons and a Bonferroni correction) in Bydureon plus dapagliflozin versus dapagliflozin alone, we computed that 13 subjects in each group will provide 90% power.

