### COMPARISONS during initial 3-H-glucose turnover study

Byetta/Dapa vs Dapa  
vs Byetta  
vs Placebo

Dapa vs Byetta  
vs Placebo

Byetta vs Placebo

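### The alphas in the three sample-size calculations are wrong as printed (0.005 given as 0.5/10; 0.167 used where a three-way split of 0.05 is 0.0167), and the stated 90% power cannot be checked until the meaning of the SD 0.34 is given

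*Combined protocol and SAP*

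**What the plan says.** All three calculations rest on the same published result: a dapagliflozin-minus-placebo difference in last-hour EGP of 0.70 ± 0.34 (mean ± SD). The target is half of that difference, for the combination against dapagliflozin alone.

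- **Study A, Sample Size Calculation.** "To detect a 50% decrease in the difference at alpha = 0.005", with the bracket 0.5/10 and the explanation "split alpha for up to 10 multiple comparisons and a Bonferroni correction". The result is that "we computed that 17 subjects in each group provided 90% power", raised to 20 for 15% loss to follow-up.
- **Studies B and C, Sample Size Calculation** (both paragraphs stand after the Study C heading). "To detect a 50% decrease in the difference at alpha = 0.167", with the bracket 0.5/3 and the explanation "split for 3 comparisons and a Bonferroni correction". The result is 13 per group for 90% power.
- **Study A, Data Analysis and Statistical Methods.** One primary comparison is named: "The following primary comparison will be performed: (i) the change in EGP above baseline following dapagliflozin alone versus dapagliflozin/exenatide". The secondary EGP comparisons are exenatide alone against the combination, and "the change in EGP above baseline following dapagliflozin alone, exenatide alone, and dapagliflozin/exenatide versus the change in EGP following placebo". That makes one primary and four secondary comparisons. Post hoc tests get a Bonferroni correction, but neither the family nor the test alpha is given, and the primary comparison is not exempted.
- **Comparisons page after the study design diagram.** Six pairs are listed for the initial turnover study. The added one is "Dapa vs Byetta".

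**The concern.** An alpha in a sample-size paragraph should be traceable: overall level, number of comparisons, quotient. Here it is not. In Study A the quotient and the alpha disagree by a factor of ten. In Studies B and C the quotient is computed correctly, but from 0.5 rather than 0.05, so the alpha that results is not a Bonferroni share of 0.05.

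The number per group depends strongly on alpha, so a factor of ten raises the question of which value was used to get 17 and 13. That could be settled by recomputing if the other inputs were clear, but the key one is not. The figure 0.34 is attached to a difference between treated groups, without saying whether it is the spread between subjects within an arm or the SD of a difference. The stated 90% power for the comparison that Study A is built on turns on that.

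**Working it through.** **Inputs.** Difference to detect: 0.5 × 0.70 = 0.35. SD figure: 0.34. Stated sizes: 17 per group (A) and 13 per group (B, C), both for 90% power. Assumed, because not stated: two independent groups, two-sided test.

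**Step 1, the alphas.**
- Study A: 0.5/10 = 0.05, while 0.05/10 = 0.005. The value 0.005 is the right ten-way split of 0.05, and only the bracket is wrong.
- Studies B and C: 0.5/3 = 0.167, while 0.05/3 = 0.0167. The alpha is ten times too large.
- Dropout: 17/0.85 = 20, which is correct.

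**Step 2, the plan's own sizes.** Normal formula: n per group = 2 (z for alpha + z for power)² SD² / 0.35², with z for 90% power = 1.282. Two readings of 0.34 are tried:
- per-subject SD = 0.34;
- 0.34 is the SD of a difference between two independent subjects, so per-subject SD = 0.34/√2 = 0.24.

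| Alpha (two-sided) | z for alpha | n, SD 0.34 | n, SD 0.24 | Stated |
|---|---|---|---|---|
| 0.005 (A) | 2.807 | 31.5, so 32 | 15.8, so 16 | 17 |
| 0.0167 (B, C) | 2.394 | 25.5, so 26 | 12.7, so 13 | 13 |
| 0.167 (B, C as printed) | 1.383 | 13.4, so 14 | 6.7, so 7 | 13 |

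Example, Study A with SD 0.34: 2 × (2.807 + 1.282)² × 0.34²/0.35² = 31.5.

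The pair 0.005 and 0.0167 with SD 0.24 comes close to both stated sizes with one sidedness throughout. The literal quotients with SD 0.34 also come close, but only by mixing sidedness: one-sided 0.05 gives 17 for Study A (16.2 rounded up), while two-sided 0.167 gives 14 for B and C. One-sided 0.167 would give 10.

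**Step 3, power by two-sided t-test (noncentral t).**

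| Setting | SD 0.24 | SD 0.34 |
|---|---|---|
| A, 17 per group, 0.005 | 88% | 50% |
| A, 20 per group, 0.005 | 94% | 61% |
| B and C, 13 per group, 0.0167 | 86% | 53% |
| B and C, 20 per group, 0.0167 | 98% | 77% |

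With the error term pooled over four arms, Study A at 17 per group and 0.005 rises to 90% (SD 0.24) or 54% (SD 0.34). With SD 0.34, 90% power at 0.005 by t-test needs 34 per group.

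If 0.34 were instead the SD of a within-subject difference, the per-subject SD would be 0.34/√(2(1 − ρ)), and ρ is not given. As an assumed range, ρ = 0.25 gives SD 0.28 and 74% power at 17 per group and 0.005; ρ = 0.5 gives 0.34 and 50%; ρ = 0.75 gives 0.48 and 21%. So 0.24 and 0.34 are illustrations, not bounds.

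**The case against.** The strongest reply is that these are decimal slips. In Study A the working value, 0.005, is right for a ten-way split. The intended alphas with SD 0.24 give 15.8 and 12.7 by the normal formula and 90% at 17 per group with four-arm error, so the sizes probably came from the correct alphas. That is the more coherent reading, and it is why the point is minor. It remains an inference: no single method gives both 17 and 13 exactly, and the plan does not say that 0.34 is the SD of a difference.

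Three stronger readings are tempting, and the documents do not support them.

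- *The ten-way split costs the primary comparison power.* The plan fixes power at 90% and solves for n, so a stricter planning alpha raises n. Power is lost only at a fixed n and only if 0.005 is also the test alpha, which the analysis section does not say. One prespecified primary comparison could use the full 0.05, but sizing it more strictly is conservative.
- *Ten contradicts the lists of five or six EGP comparisons.* The text says up to 10, which is a ceiling. At 0.005 each, five or six comparisons use at most 2.5% or 3% familywise error.
- *Studies B and C would run at 50% familywise error* (3 × 0.167), *with 13 per group.* The paragraphs set no test alpha and call the split a Bonferroni correction. The Study A arms of 20 are planned to carry forward, and placebo subjects may join them.

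**Conclusion.** The printed alphas are wrong: the bracket in Study A, and the alpha itself, by a factor of ten, in Studies B and C. This holds by arithmetic alone, given an overall level of 0.05, the only level at which 0.005 is a ten-way split.

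The sizes 17 and 13 are not shown to be wrong. If the per-subject SD is 0.24, Study A has roughly its stated power (88% to 90% at 17 completers) and Studies B and C are slightly short at 13 (86%) but well covered at 20 (98%). If the per-subject SD is 0.34, the stated 90% fails: about 50% in Study A at 17, and 53% in Studies B and C at 13 or 77% at 20. These figures assume a two-sided comparison of independent groups and a true difference of 0.35.

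Severity is minor, unless 0.34 proves to be the per-subject SD. In that case the power claim for the primary comparison needs real revision.

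**What to change.** 1. In the Study A sample-size paragraph, change 0.5/10 to 0.05/10. In the Study B and C paragraphs, change 0.167 (0.5/3) to 0.0167 (0.05/3).
2. State whether 0.34 is a per-subject SD or the SD of a difference (and of which kind), the test, and its sidedness.
3. Restate the power at the corrected alphas for 17 and 13 per group, and for 20.
4. In Study A's Data Analysis and Statistical Methods, state the Bonferroni family and the alpha for the primary comparison. Reconcile the five EGP comparisons there with the six pairs on the comparisons page, and say whether the three other secondary end points belong to the family.

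This adds no patients and changes only text. The possible cost is that the restated power falls below 90%.

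Optional, as the sponsor's design choice: test the single primary comparison at two-sided 0.05 and the secondary EGP comparisons only if it is significant. At 17 per group the primary comparison would then have 98% power (SD 0.24) or 83% (SD 0.34). The price is that every secondary EGP test, including the contrasts with placebo, becomes conditional on one result. With SD 0.34 this alone does not restore 90%.

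### The alphas in the sample size paragraphs are wrong as written: Study A derives 0.005 from 0.5/10, and Studies B and C print 0.167 (=0.5/3) where a Bonferroni split of 0.05 over 3 gives 0.0167

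*Combined protocol and SAP*

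**What the plan says.** Study A, Sample Size Calculation, takes its inputs from the sponsor's published results: "the difference in the rate of basal EGP during the last hour of EGP measurement in dapagliflozin-treated and placebo-treated individuals was" 0.70 ± 0.34 (mean ± SD). The target and threshold follow: "To detect a 50% decrease in the difference at alpha = 0.005", with the bracketed working 0.5/10 and the explanation "split alpha for up to 10 multiple comparisons and a Bonferroni correction". The result is "we computed that 17 subjects in each group provided 90% power", raised to 20 for 15% loss.

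Two further sample size paragraphs stand under the Study C heading. One concerns Byetta (Study B) and the other Bydureon (Study C). Both use the same 0.70 ± 0.34. The Byetta paragraph reads "To detect a 50% decrease in the difference at alpha = 0.167", with the working 0.5/3 and the explanation "split for 3 comparisons and a Bonferroni correction", and concludes: "in Byetta plus dapagliflozin versus dapagliflozin alone, we computed that 13 subjects in each group will provide 90% power". The Bydureon paragraph repeats the same alpha, quotient and group size.

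Study A, Data Analysis and Statistical Methods, defines what is compared: "The following primary comparison will be performed: (i) the change in EGP above baseline following dapagliflozin alone versus dapagliflozin/exenatide". No sample size paragraph states the test, the sidedness, or the SD of that change-from-baseline variable.

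**The concern.** In Study A the printed alpha and its printed derivation differ by a factor of ten. The same numerator appears in all three sample size paragraphs, so this is unlikely to be a fault of PDF conversion. In Study A it leaves the alpha intact. In Studies B and C the stated alpha follows the wrong numerator, so the threshold on which 13 per group is said to rest is itself wrong. Used as printed, it would allow a summed error of 3 × 0.167 = 0.50 over the three comparisons, which defeats the correction that the paragraphs invoke.

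There is a second, lesser question. Power depends on the SD within each arm of the variable compared. The plan attaches 0.34 to a difference between treatments and does not carry it through to an arm SD. The comparison at stake in Study A is the one named as primary.

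**Working it through.** **Inputs.** From the sample size paragraphs: mean difference 0.70, SD 0.34, a 50% decrease, power 90%, 17 per group (Study A) and 13 per group (Studies B and C). Assumptions, because the plan gives none: two-sided tests and a two-group comparison of means. Where the error is pooled over k arms, df = k(n − 1).

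**Step 1: the quotients.**
- 0.5/10 = 0.05, whereas 0.05/10 = 0.005 (the alpha printed for Study A).
- 0.5/3 = 0.167 (the alpha printed for Studies B and C), whereas 0.05/3 = 0.0167.

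**Step 2: reproduce Study A.** The difference to detect is δ = 0.5 × 0.70 = 0.35. If 0.34 is the SD of a difference between two independent persons, the arm SD is σ = 0.34/√2 = 0.2404.

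Normal formula: n = 2σ²(z₁₋α/₂ + z₀.₉₀)²/δ². At 0.005 this is (2.807 + 1.282)² × (0.34/0.35)² = 15.8, so 16 per group. By the t-test, 18 are needed with two groups and 17 with error pooled over four arms. Power at 17 per group:

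| Method | Power |
|---|---|
| Two-group t, 32 df | 88.0% |
| Four-arm pooled error, 64 df | 90.4% |
| Normal approximation | 92.5% |

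The stated 17 and 90% are therefore reproduced, and 17/0.85 = 20 is correct.

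**Step 3: the same reading in Studies B and C** (δ = 0.35, σ = 0.2404):

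| Alpha | n for 90%, normal | n for 90%, two-group t | Power at 13 |
|---|---|---|---|
| 0.0167 | 12.7, so 13 | 15 | 86.3% (two-group t), 87.9% (three-group pooled), 90.6% (normal) |
| 0.167 | 7 | 8 | 98.8% (two-group t), 99.0% (normal) |

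The stated 13 matches 0.0167 and is far from what 0.167 would require.

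**Step 4: does a literal reading of the quotients fit both sizes?** With per-arm SD 0.34, n for 90% is as follows (stated: 17 and 13):

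| Alpha | Study A | Studies B and C |
|---|---|---|
| 0.5/k, one-sided | 17 | 10 |
| 0.5/k, two-sided | 20 to 21 | 14 |
| 0.05/k, two-sided | 32 to 34 | 26 to 27 |

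Each literal reading comes close to one stated size and misses the other. Arm SD 0.24 with 0.05/k gives 16 to 18 and 13 to 15, which covers both.

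**Step 5: sensitivity of Study A to the arm SD** (two-sided 0.005; range from two-group t to four-arm pooled error):

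| Arm SD | Power, 17 per group | Power, 20 per group |
|---|---|---|
| 0.24 | 88.0 to 90.4% | 94.0 to 95.3% |
| 0.34 (scenario only) | 50 to 54% | 61 to 64% |

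The largest arm SD that still gives 90% is 0.234 to 0.242 with 17 per group, and 0.257 to 0.264 with all 20.

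**The case against.** The strongest reply is that these are misprints with no effect on the trial. Study A's alpha is correct, its size reproduces, and 13 per group fits 0.0167, so the author evidently calculated with the right value. Nor does the analysis text for Studies B and C specify any test at 0.167. Much of this stands. Study A's type I error is not affected by the numerator, and the sum of 0.50 would arise only if someone applied the printed threshold. But 0.167 is the only alpha that the plan gives for those two studies, and their stated size is said to rest on it. Moreover, 13 alone does not identify the intended alpha: at 0.167 with per-arm SD 0.34 it would give 88 to 89% power. It takes both studies together to see what was probably meant.

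On the SD, a reader might infer that Study A really has only about 50% power. The documents do not support that. They attach 0.34 to the difference, not to an arm, and on that wording the stated 17 reproduces. The 50 to 54% needs a reading that the text does not make. The agreement does not prove that 90% is delivered either. A two-group formula with per-arm SD 0.34 and its factor of 2 left out is algebraically identical to using 0.34/√2, so the stated sizes cannot tell the two apart. A change from baseline may also have an SD unrelated to 0.34, and any arm SD up to about 0.24 would give 90%. What is missing is a definition; no power deficit has been shown.

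**Conclusion.** The alpha figures are wrong as written. In Study A the error is confined to the quotient. In Studies B and C the stated threshold is ten times the Bonferroni share of 0.05 over three comparisons. With arm SD 0.24 and two-sided tests, the power of 13 per group at the correct 0.0167 is 86 to 88% by t and 91% by normal approximation, so the stated 90% is at most slightly optimistic.

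The point about the SD is secondary and conditional. Study A's 90% is supported if 0.34 is the SD of a difference between two independent persons, and it remains unconfirmed for the change-from-baseline variable actually compared. The per-arm 0.34 figures are one scenario, not a finding about this trial.

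**What to change.** 1. In Study A, Sample Size Calculation, replace 0.5/10 with 0.05/10 and keep alpha at 0.005.
2. In both 13-per-group paragraphs, replace 0.167 (=0.5/3) with 0.0167 (=0.05/3), and restate the power of 13 per group at that alpha.
3. State what 0.34 measures, and give the arm SD of the change in EGP from baseline, the test and the sidedness. The sponsor should check that SD against its own published data. If it exceeds about 0.24, restate Study A's power for 17 and for 20 per group.

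The cost is a text correction and a short recalculation from data that the sponsor should hold. Enrolment and analysis stay as they are. The downside is that the restated power may fall slightly below 90%, or further if the arm SD proves well above 0.24.
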